### 10 STATISTICAL ANALYSIS

### 10.1 Analysis of Data/Study Outcomes

### 10.1.1 Safety Population

The Safety Population will consist of all enrolled subjects receiving any parotid saline irrigation used to determine parotid filling volume during Stage I screening.

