#### 2.2 Secondary Objectives

Secondary objectives of the study include the following:

• To perform mechanistic studies to determine the mechanisms of action of low-dose topical corticosteroid irrigation of the parotid gland.

- To assess biomarkers of inflammation and salivary gland dysfunction in SS subjects treated with low-dose topical corticosteroid irrigation of the parotid glands.
- To assess localized safety of dexamethasone irrigation of the parotid gland, as compared with placebo.

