## **3 SUBJECTS**

## 3.1 **Description of Study Populations**

The study will enroll up to 20 adult female subjects with primary SS, a focus score of  $\geq 1$  on minor salivary gland (MSG) biopsy in the previous 7 years, and measurable bilateral parotid salivary flow ( $\geq 0.01$  mL/min per gland) to randomize and treat 16 subjects.

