#### 3.3 Exclusion Criteria

- 1. History of lymphoma.
- 2. History of mycosis, aspergillosis, or other deep fungal infection of the parotid gland.
- 3. History of salivary gland malignancy (primary or metastatic to the salivary gland).
- 4. History of secondary Sjögren's syndrome.
- 5. Parotid infection that does not resolve at least 4 weeks before the start of Screening.
- 6. Any active viral infection that does not resolve by the start of Screening.
- 7. Pregnancy or lactation.
- 8. Use of biologics within 3 months of the start of Screening.
- 9. Any experimental therapy within 3 months before the start of Screening.
- Use of immunosuppressants such as methotrexate, leflunomide, azathioprine, cyclophosphamide, systemic cyclosporine, or systemic corticosteroids within 3 months prior to the start of the Screening.
- 11. Use of inhaled corticosteroids within 3 months prior to the start of Screening.
- Use of antimalarials and regular use of NSAIDs unless the dose has been stable (or decreased) for at least 2 months.
- Inability to discontinue the use of saliva stimulants such as pilocarpine and cevimeline for 24 hours before each study visit.
- 14. Parotid intraductal irrigation or instillation with steroids within the past year.

- 15. Use of rituximab within 6 months prior to the start of Screening.
- 16. Allergy to steroids or technetium, or any components of the formulations.
- 17. Current use of warfarin or heparin.
- 18. History of bleeding disorder.
- 19. Both severe atrophy and fibrosis of the MSG noted on the pathology report of the MSG biopsy.
- 20. Inability to comply with protocol procedures and the number of required visits.
- 21. Inability to cannulate one or both parotid glands.
- 22. Parotid fill volume <0.5 mL in one or both parotid glands.
- 23. Significant concurrent medical condition or other circumstances that, in the opinion of the principal investigator, could affect the subject's ability to tolerate or complete the study.
- 24. Unable to understand written English for completion of study questionnaires.

The eligibility checklist is included in Appendix 24.3.

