6	Baseline ultrasound-guided core needle biopsy will be performed at least 14 days before Day 0. Follow-up biopsy will be performed after the technetium and magnetic resonance imaging scans on Day 56.									
7	Complete blood count with differential and platelets, Chem 14, erythrocyte sedimentation rate, C-reactive protein, and amylase. Prothrombin time and partial thromboplastin time will be obtained at Stage II screening and Day 56. The completed blood count with differential and platelets, prothrombin time, and partial thromboplastin time must be done with 7 days before ultrasound-guided core needle biopsy of the parotid. Clinical laboratory tests will be performed at the Safety Follow-up only if clinically indicated.									
8	Antinuclear antibodies, antibodies to extractable	nuclear antigens, rheuma	toid factor, C3 complement	nt, C4 complement, imm	nunoglobulin (Ig)A,	IgM, and IgG.				
9	Two samples will be obtained: one prior to rando treatment.	mized irrigation treatme	nt of the parotid glands (ba	aseline) and the other 7	5 ( $\pm$ 15) minutes afte	r irrigation				
10	Performed as final step of Stage I, when subject h	as otherwise qualified for	or the study.							
11	Performed as final step of Stage II, when subject	has otherwise qualified	for the study.							
12	2 Performed if a minor salivary gland biopsy is needed based on criteria in Section 3.2. Must be conducted and evaluated prior to any other procedures and activities associated with Stage II screening.									
13	3 On Days 0 and 28, obtained prior to irrigation treatment.									
14	Assessed via telephone. Clinic visit scheduled, if	deemed necessary based	l on medical need or per su	ıbject request.						
15	Performed only if clinic visit deemed necessary pe	er telephone interview.								

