#### 9.2 Secondary Outcome Measures

Secondary endpoints include the following:

- Change in focus score on parotid biopsy from Stage II screening to Day 56.
- Changes in salivary flow from Day 0 to study Days 14, 28, 42, and 56.
- Changes in assessments on the Patient Dry Mouth Questionnaire from Day 0 to study Days 14, 28, 42, and 56.
- Changes in assessments on the Sjögren's Disease Activity Index from Day 0 to study Days 14, 28, 42, and 56.
- Changes in other assessments of salivary function from baseline to study Day 56, including technetium scan of the salivary glands.
- Changes in laboratory measures of inflammation.
- Frequency of AEs related to treatment; location of the AE (body site, right or left), will be recorded and evaluated, as applicable.

Exploratory endpoints will be the changes in mechanistic endpoints from baseline to study Days 14, 28, 42, and 56.

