Approximately 20 subjects will be screened to ensure that 16 subjects will be randomized and treated with dexamethasone irrigation. Subjects who discontinue from the study before the Stage I screening parotid irrigation will be replaced. Subjects who do not receive the first irrigation treatment and at least 1 post-treatment salivary flow assessment will also be replaced.

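### The only Safety Population is defined by the screening saline irrigation, so subjects never given a randomised irrigation can sit in the denominator of the treatment-related adverse event rates

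*Protocol*

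**What the plan says.** Section 10.1.1 gives the protocol's one safety set: "all enrolled subjects receiving any parotid saline irrigation used to determine parotid filling volume during Stage I screening". Membership does not require any randomised irrigation.

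The safety objective in section 2.2 is "To assess localized safety of dexamethasone irrigation of the parotid gland, as compared with placebo". The matching endpoint in section 9.2 is "Frequency of AEs related to treatment; location of the AE (body site, right or left), will be recorded and evaluated, as applicable".

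On numbers, section 3.1 says "The study will enroll up to 20 adult female subjects with primary SS", and section 10.2 says "Approximately 20 subjects will be screened to ensure that 16 subjects will be randomized and treated with dexamethasone irrigation". Section 10.2 also provides for replacement: "Subjects who do not receive the first irrigation treatment and at least 1 post-treatment salivary flow assessment will also be replaced".

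On timing, section 4.3 and Table 4-1 place the saline irrigation and fill-volume measurement at the end of Stage I. Stage II follows, with MRI, technetium scan and parotid biopsy, and randomisation and the first randomised irrigation come on Day 0. One exclusion in section 3.3 is "Parotid fill volume <0.5 mL in one or both parotid glands"; another is failure to cannulate a gland.

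**The concern.** The population does not match the question it serves. The objective compares glands given dexamethasone with glands given placebo. A subject who leaves after the fill-volume test has neither, so she can add to the denominator of a treatment-related rate but never to its numerator.

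Such subjects are foreseeable. The irrigation that admits a subject to the Safety Population is also the test for the fill-volume exclusion, so the procedure that rules her out of the trial also puts her in the safety set. Up to six weeks of Stage II procedures then lie between the irrigation and Day 0. Section 10.2 replaces subjects who miss the first treatment irrigation, but section 10.1.1 keeps them in the safety set if they were irrigated at screening.

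Reading "enrolled" as "randomised" does not remove the problem. Section 4.3 equates enrolment with the Stage I screening visit, and section 3.1 separates the 20 enrolled from the 16 randomised and treated.

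At stake are the absolute frequencies of local harm, which are a main safety output of a 16-subject pilot.

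**Working it through.** The protocol states no safety rate, safety bound or safety power, so there is no figure of its own to reproduce. The check is of the denominator.

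**Inputs**
- Treated subjects: 16 (sections 3.1 and 10.2).
- Enrolled or screened: up to, or approximately, 20 (sections 3.1 and 10.2).
- Irrigated at screening but never treated, *k*: not given. I take *k* = 0 to 4, the ceiling being 20 − 16 = 4.
- Each treated subject has one dexamethasone gland and one saline gland (section 4.1).

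**Step 1: dilution factor.** With *x* subjects having a treatment-related event in the gland concerned, the rate on treated subjects is *x*/16 and the rate on the Safety Population is *x*/(16 + *k*). The second divided by the first is 16/(16 + *k*), whatever *x* is.

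| *k* | Safety Population | Factor | Relative understatement | 1 event shown as | 4 events shown as |
|---|---|---|---|---|---|
| 0 | 16 | 1.00 | 0% | 6.3% | 25.0% |
| 1 | 17 | 0.94 | 6% | 5.9% | 23.5% |
| 2 | 18 | 0.89 | 11% | 5.6% | 22.2% |
| 3 | 19 | 0.84 | 16% | 5.3% | 21.1% |
| 4 | 20 | 0.80 | 20% | 5.0% | 20.0% |

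**Step 2: the comparison between treatments.** Suppose, for illustration, that 5 subjects have an event only in the dexamethasone gland and 1 only in the placebo gland.
- On 16: 5/16 = 31.3% against 1/16 = 6.3%, a risk difference of 4/16 = 25 points.
- On 20: 5/20 = 25.0% against 1/20 = 5.0%, a risk difference of 4/20 = 20 points.
- Rate ratio: 5/1 = 5.0 on either denominator.
- Exact McNemar test: it uses only the 6 discordant subjects, so two-sided p = 2 × (1 + 6)/2⁶ = 14/64 = 0.219 on either denominator.

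The untreated subjects enter both sides equally. They shrink the absolute rates and the risk difference, and leave the relative and paired contrasts alone.

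**Step 3: how large *k* can be.** Four is a ceiling. Subjects failing on salivary flow, laboratory tests or minor salivary gland biopsy leave before the irrigation. Failed cannulation may mean that no saline was given. A subject who was treated but replaced for want of a later flow measurement counts towards the 20 but is not untreated.

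**The case against.** The strongest reply is that section 10.1.1 only says who is in the set. Nothing in section 10 names it as the denominator for adverse events by treatment, and table denominators and onset windows are commonly left to the SAP, which is not at hand. A gland-by-treatment table has no gland to count for an untreated subject, so a sensible programmer might leave her out. The broad set also has a purpose: section 7.3 lists duct trauma, infection and nerve damage as risks of irrigation, including the first, saline-only one, and section 8 monitors subjects from consent.

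Most of this stands, and it limits the point without removing it. The size is conditional on the set being used as the denominator. But the population is fixed in the protocol, is the only one for safety, and does not fit the stated comparison. The Secondary Efficacy Population in section 10.1.3 does require an on-treatment irrigation, but it cannot stand in, because it also demands a later salivary flow measurement.

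A reader might go further and infer that events from the screening irrigation and the Stage II biopsy are pooled with treatment events. The documents do not support that: the endpoint is limited to events related to treatment, which should keep most earlier events out of the numerator. A reader might also infer that the comparison is tilted towards dexamethasone, or that a safety bound or stopping rule is weakened. The dilution is equal on both sides, the protocol states no safety bound, and the alerts in section 15.3 are counts that no denominator affects.

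**Conclusion.** The point holds in a limited form. The protocol's one safety set admits subjects who never receive a randomised irrigation, while its safety objective and endpoint concern randomised treatment. Used as the denominator, it understates absolute treatment-related adverse event rates and the risk difference by 6% to 20% in relative terms for 1 to 4 untreated members, and by nothing if there are none. For a single event the most that can be lost is 6.3% − 5.0% = 1.3 percentage points.

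This rests on 16 treated subjects, no more than 20 enrolled, and the set being used as written. The primary analysis is not involved. The mismatch should be corrected because it is foreseeable and cheap to remove, not because it could change the direction of the safety comparison.

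**What to change.** Keep the present set and label it for harms of the screening procedures. Add a treated safety set: all subjects who received at least one randomised irrigation, with no requirement for a later flow measurement. Base the dexamethasone-versus-placebo adverse event frequencies on it, counting events with onset after the Day 0 irrigation and tabulating them by gland according to the treatment that gland actually received.

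The cost is one further definition and one further table. Reported absolute rates will be slightly higher than on the broader set. No visit, procedure or sample size changes.

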### 10.1.2 Primary Efficacy Population

The Primary Efficacy Population (PEP) will consist of all enrolled subjects who receive all parotid irrigations on study Days 0 and 28, have the same treatment applied to the same parotid

(regardless of random assignment) at both visits, and have values for the primary endpoint (i.e., change in salivary flow from Day 0 to Day 56). The PEP will be used in the primary analysis.

#### 10.1.3 Secondary Efficacy Population

The Secondary Efficacy Population (SEP) will consist of all enrolled subjects who receive at least one on-treatment set of parotid irrigations and have at least one salivary flow assessment after study Day 0. The SEP will be used in some secondary analyses.

#### 10.1.4 Demographic and Baseline Characteristics

Demographic and baseline characteristics will be summarized in tables. Continuous demographic and baseline variables will be summarized as means, medians, SDs, minimum values, and maximum values. Categorical demographic (e.g., race) and baseline variables will be summarized as frequencies and percents. Baseline variables pertaining to the parotid gland will be summarized by their assigned treatment. Differences between parotid glands by side of the body (right or left) and assigned treatment will be estimated with 90% confidence intervals.

### 10.1.5 Primary Efficacy Analysis

The primary analysis will compare the change from Day 0 in salivary flow in the dexamethasone-irrigated parotid glands (active treatment) with the saline-irrigated parotid glands (placebo treatment) at study Day 56. The treatment effects on the change from Day 0 will be analyzed using repeated measures with change from Day 0 to Day 56 as the dependent variable with random effects for subjects. Day 0 salivary flow will be included as a covariate to adjust for any possible effects of baseline salivary flow on the degree to which salivary flow can change from Day 0. Statistical inferences for treatment effects on salivary flow will be 1-sided ( $\alpha$ =0.05) and test for increased salivary flow in the dexamethasone-irrigated parotid glands compared with the saline-irrigated parotid glands. The estimate of the treatment effect will be reported with the associated 1-way confidence interval. The primary analysis will be performed on the PEP.

### 10.1.6 Secondary Analyses of Salivary Flow

Secondary analysis of salivary flow will test for increased salivary flow in the dexamethasoneirrigated parotids compared with the saline-irrigated parotids with respect to change from Day 0 at each of the remaining study days (study Days 14, 28, and 42).

The treatment effects on the change from Day 0 will be analyzed as doubly-repeated measures with change from Day 0 as the dependent variable, random effects for subjects, and repeated effects for treatment and post-Day 0 study day. Day 0 salivary flow will be included as a covariate to adjust for any possible effects of baseline salivary flow on the degree to which salivary flow can change from Day 0. Statistical inferences for treatment effects on salivary flow will be 1-sided ( $\alpha$ =0.05) and test for increased salivary flow in the dexamethasone-irrigated parotid glands compared with the saline-irrigated parotid glands. Contrast statements within doubly-repeated measures design will be used to compare the treatment effects on the change in salivary flow from Day 0 at study Days 14, 28, and 42. If significant treatment effects are found at any of the study days, then additional secondary analyses will test for pair-wise differences in change from Day 0 salivary flow between the study days. These tests for pair-wise differences in salivary flow between study days will use 2-sided tests since it is desirable to test for both negative and positive differences (e.g., it is of interest to test whether change in salivary flow from Day 0 to Day 42 is greater than or less than the change in salivary from Day 0 to Day 28). These secondary analyses will be performed on the SEP, with any endpoints following the second on-treatment irrigation set to missing, if the second on-treatment irrigation was discordant with the first treatment irrigation.

The Patient Dry Mouth Questionnaire and the Sjögren's Disease Activity Index will be summarized for each question and at each visit using frequencies and percents. Questions pertaining to symptoms of SS (e.g., difficulty chewing food, changes in rate of tooth decay, mouth dryness, etc.) will be displayed graphically over time as frequencies for binomial and categorical outcomes, and as medians for ordinal outcomes. Binomial- and ordinal-scaled symptoms of SS will be further summarized by visit as change from baseline (Day 0) using shift tables. Shifts from baseline in frequencies or ordinal values that appear substantial will be further analyzed using the McNemar's test. If the data appears rich enough, further longitudinal analysis may be performed using generalized estimating equations (GEE). Any p-values reported from the McNemar's test or GEE analyses will be considered exploratory.

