#### 10.1.8 Criteria for Significance

The hypothesis test and confidence interval of treatment effects for the primary analysis will be one-sided and test for a positive treatment effect. Hypothesis tests and confidence intervals of secondary analyses will be either 1- or 2-sided as described above. All statistical tests will use an  $\alpha = 0.05$ .

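### McNemar's test is named for ordinal as well as binary symptom shifts, and is run only on shifts that look large (minor)

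*Protocol*

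**What the plan says.** Protocol Section 9.2 lists as a secondary endpoint "Changes in assessments on the Patient Dry Mouth Questionnaire from Day 0 to study Days 14, 28, 42, and 56", with a parallel entry for the Sjögren's Disease Activity Index.

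The analysis is in the questionnaire paragraph of Section 10.1.6. Each question is summarised at each visit. Symptom items are graphed over time, as frequencies for binomial and categorical items "and as medians for ordinal outcomes". Then: "Binomial- and ordinal-scaled symptoms of SS will be further summarized by visit as change from baseline (Day 0) using shift tables".

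Testing follows: "Shifts from baseline in frequencies or ordinal values that appear substantial will be further analyzed using the McNemar's test". A longitudinal GEE analysis is possible if the data allow it. The paragraph closes: "Any p-values reported from the McNemar's test or GEE analyses will be considered exploratory".

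Section 10.1.8 applies 0.05 throughout ("All statistical tests will use an" α of 0.05). On sidedness it says "Hypothesis tests and confidence intervals of secondary analyses will be either 1- or 2-sided as described above", but Section 10.1.6 gives no side for the questionnaire tests.

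**The concern.** Two features of the testing sentence do not work as written.

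First, one test is assigned to two kinds of data. McNemar's test compares the two discordant cells of a paired two-by-two table. For an ordinal item it can be used only after a cut turns the scale into two levels. A subject who improves by several grades without crossing the cut then counts as unchanged, and a one-grade change across the cut counts the same as a four-grade change. The same paragraph respects the ordering when it describes the data (medians, shift tables) and drops it when it tests.

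Second, whether a test is run depends on the observed size of the shift ("ordinal values that appear substantial will be further analyzed"), which is the quantity the test assesses. No threshold is given, so the reported p-values come from a set already selected for large shifts.

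At stake is the reading of two patient- and clinician-rated secondary endpoints in a 16-subject pilot. A real ordinal improvement may go unsupported, and a chance one may look better supported than it is.

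**Working it through.** The protocol gives no power, effect size, number of levels or cut for these tests, so there is no figure of its own to reproduce. What follows is illustrative.

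**Inputs from the protocol:** 16 subjects (Section 10.2), α = 0.05 (Section 10.1.8), McNemar's test for ordinal values (Section 10.1.6).

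**Assumed inputs:** two-sided tests; five equally likely levels at Day 0, generated from a latent normal variable; correlation 0.6 between Day 0 and the visit; shift of 0.7 or 0.9 latent SD; eight items for the selection check.

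**Step 1: what exact McNemar needs.** If all m discordant pairs go one way, the two-sided p-value is 2 × 0.5^m. For m = 5 this is 0.0625; for m = 6 it is 0.031. At least 6 of the 16 subjects must cross the cut, and with exactly 6 all must cross in the same direction.

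**Step 2: simulated power.**

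| Test | 0.7 SD | 0.9 SD |
|---|---|---|
| Wilcoxon signed-rank on the change | 70% | 88% |
| Asymptotic McNemar, best cut | 48% | 66% |
| Asymptotic McNemar, worst cut | 18% | 25% |
| Exact McNemar, best cut | 24% | 45% |
| Exact McNemar, worst cut | 2% | 4% |

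Over the two middle cuts and both shifts, asymptotic McNemar has 40–66% and exact McNemar 15–45%. At the best cut the asymptotic test keeps 48/70 = 69% and 66/88 = 75% of the signed-rank power; the exact test keeps 24/70 = 34% and 45/88 = 51%.

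**Step 3: is the gap only the conservatism of the exact test?** No. With five levels, a shift of 0.8 SD and correlation 0.5 to 0.7, exact McNemar at a mid-scale cut has power 0.32–0.34. An exact sign test on better versus worse has about 0.57–0.78, and the signed-rank test 0.73–0.89. The first two are both exact binomial tests, so that difference comes from collapsing the scale. Asymptotic McNemar in the same setting has 0.52–0.64.

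**Step 4: selection.** If the largest-looking shifts among J independent null tests are the ones tested, the chance of at least one nominal p below 0.05 is at most about 1 − (1 − a)^J, where a is the true size of each test.

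- True 5% test, J = 8: 1 − 0.95^8 = 0.34. For J = 5, 10 and 20 it is 0.23, 0.40 and 0.64.
- Exact McNemar, true size about 0.8%, J = 8: 1 − 0.992^8 = 0.06. Simulation for J = 5, 10 and 20 gives 0.03, 0.06 and 0.14.

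Seen from a single selected item: if there is no true change but a net shift of at least 4 of 16 subjects is observed, the probability of p ≤ 0.05 is 0.48 for asymptotic and 0.07 for exact McNemar.

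**The case against.** The strongest reply is that little rests on these tests. The protocol declares their p-values exploratory. It also commits, without selection, to summarising every question at every visit and to graphs and shift tables for symptom items, so an ordinal improvement will be visible whether or not it is tested. GEE is available as a further analysis. McNemar is the right test for the binary items in the same sentence. A cut-point, or the choice between exact and asymptotic versions, could properly sit in an analysis plan that is not at hand.

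A further reply is that a better test gains little. Each subject receives both dexamethasone and saline, and both instruments are completed per subject, not per gland (Sections 4.4.4 and 4.4.5). A before-after change therefore has no placebo contrast, and more power would not show a dexamethasone effect.

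Most of this stands and sets the severity. It does not remove the point. The protocol itself names a binary test for ordinal values, and any later choice of cut would still discard the size of the shift. The exploratory label lowers the weight of a p-value; it does not restore an error rate lost through selection.

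A reader might also be tempted to put the low exact-test power beside the 34% selection figure. They describe different tests. The exact test has the larger power loss but a selection risk of about 6%; the 34% needs a true 5% test, for which the power loss is smaller.

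**Conclusion.** The point holds as a minor one. McNemar's test does not fit the ordinal items to which Section 10.1.6 assigns it, and running it only on shifts that look large leaves the p-values without their nominal error rate. The loss of power appears at every cut examined, but its size depends on the version of the test, the cut, the number of levels, the correlation and the shift, none of which the protocol states.

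Two stronger readings are not supported. One is that the plan loses most of the power. That is true of the exact test in many settings and of a badly placed cut, but not of the asymptotic test at a mid-scale cut, which keeps roughly two-thirds to three-quarters of the signed-rank power at its best cut in the main setting. The other is that the p-values are uninterpretable. They are labelled exploratory and will stand beside full descriptive summaries, so they can be read with that caution.

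The selection figures assume independent items. The questionnaire itself is in an appendix not reproduced in the document, so the count of eight is an assumption. No primary or confirmatory inference is affected.

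**What to change.** Amend the testing sentence in Section 10.1.6 as follows:

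- keep McNemar's test for binary symptom items only;
- for ordinal items, use the Wilcoxon signed-rank test on change from Day 0, or the sign test if ranking the sizes of change across levels is not thought sensible;
- replace selection by appearance with a pre-listed set of symptom items and visits, tested however the shift looks;
- keep the statement that these p-values are exploratory.

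The cost is a sentence or two of protocol text and a little more analysis work. The downside is more nominal p-values, all to be read as exploratory. The change does not supply a placebo comparison, so a finding on these items would still describe change over time and not an effect of dexamethasone.
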